This section presents the primary and secondary research questions that will be assessed in the impact evaluation of the Momentary Affect Regulation Safer Sex Intervention (MARSSI). Our classification of primary and secondary research questions aligns with categorization rules provided in the Instructions For TPP20 Tier 2 Phase II Impact And Program Implementation Evaluation Analysis Plan.¹ While the Participant Questionnaire collects data on many outcomes that may be affected by the intervention, following categorization rules, the research team has designated a select set of short-term behavioral outcomes as primary, which the program developer (in consultation with the research team) believes are most important for understanding the efficacy of MARSSI to achieve its goal of reducing unplanned pregnancy and STIs in the target population. Secondary research questions cover the broader array of outcomes measured in the Participant Questionnaire, as well as alternative analytic methods, that are designed to explore the impact of the program on other theoretically important behaviors and antecedents within the full sample and subgroups of interest.

a. Primary research questions²

1. What is the short-term impact (three months post-intervention) of the offer to participate in MARSSI (treatment) relative to the offer to participate in the control condition on participants' reported frequency of having vaginal sex without condoms in the past 30 days?
2. What is the short-term impact (three months post-intervention) of the offer to participate in MARSSI (treatment) relative to the offer to participate in the control condition on participants' reported current use of effective non-barrier contraception?
3. What is the short-term impact (three months post-intervention) of the offer to participate in MARSSI (treatment) relative to the offer to participate in the control condition on participants' reported number of sexual partners in the past 3 months?

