- l. Use of dual contraception (combined condom and effective non-barrier contraceptive use) during last vaginal sex
- m. Frequency of oral sex (in past 30 days)
- n. Frequency of anal sex (in past 30 days)
- o. Frequency of anal sex without condoms (in past 30 days)
- p. Frequency of using alcohol or drugs before having any type of sex (vaginal, anal, or oral) (in past 30 days)
- q. Pregnancy ambivalence*

3. What are the long-term (six months post-intervention period) impacts of the offer to participate in MARSSI (treatment) relative to the offer to participate in the control condition on the following sexual health behaviors, health outcomes, and theoretical antecedents of sexual health and health behavior?

- a. Depressive symptoms
- b. Frequency of vaginal sex (in past 30 days)
- c. Frequency of vaginal sex without effective non-barrier contraceptive use (in past 30 days)
- d. Frequency of emergency contraception use after vaginal sex (in past 30 days)
- e. Frequency of dual contraception (combined condom and effective non-barrier contraceptive use) during vaginal sex (in past 30 days)*
- f. Use of effective non-barrier contraception during last vaginal sex
- g. Use of condoms during last vaginal sex
- h. No effective contraception used during last vaginal sex
- i. Use of dual contraception (combined condom and effective non-barrier contraceptive use) during last vaginal sex
- j. Frequency of oral sex (in past 30 days)
- k. Frequency of anal sex (in past 30 days)
- l. Frequency of anal sex without condoms (in past 30 days)
- m. Frequency of using alcohol or drugs before having any type of sex (vaginal, anal, or oral) (in past 30 days)
- n. Current use of effective non-barrier contraception
- o. Frequency of vaginal sex without condoms (in past 30 days)
- p. Number of sexual partners (in past 3 months)

Analysis of primary and secondary outcomes in subgroups using ITT approach

What are the post-program, short-term, and long-term impacts of the offer to participate in MARSSI (treatment) relative to the offer to participate in the control condition on primary and secondary outcomes for subgroups defined by the following baseline data: 1) PHQ-8

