participants are either coded as currently using effective non-barrier contraception or not currently using effective non-barrier contraception. Data used to assess the impact of the treatment (MARSSI) on contraceptive use are obtained from the following item on the *Participant Questionnaire*, which is administered to both the treatment and control groups at baseline, short-term follow-up (three months post-intervention period), and long-term follow-up (six months post-intervention period).

- Please indicate which method of prescription birth control you are currently using.
 - Oral contraceptives (for example, the pill)
 - The patch (for example, Ortho Evra)
 - The shot/injection (for example, Depo-Provera)
 - The ring (for example, NuvaRing)
 - The implant (for example, Implanon or Nexplanon)
 - IUD (for example, ParaGard, Skyla, Mirena, Kyleena, Liletta)
 - None of the above

Persons who indicate that they are currently using any of the listed methods are considered to be currently using effective non-barrier contraception and are coded as 1. Persons who select *None* are considered to not be currently using effective non-barrier contraception and are coded as 0.

MARSSI will be considered to have a positive impact on non-barrier contraceptive use if, as compared to participants who are assigned to the control group, a larger proportion of participants who are offered MARSSI report using effective non-barrier contraception at the three-month post-intervention period and the difference between groups is statically significant.

Number of sexual partners

Number of sexual partners is constructed as a count variable – the number of sexual partners the participant reports that they have had in the past three months.²⁵ Data used to assess the impact of the treatment (MARSSI) on number of sexual partners are obtained from the following item on the *Participant Questionnaire*, which is administered to both the treatment and control groups at baseline, short-term follow-up (three months post-intervention period), and long-term follow-up (six months post-intervention period).

- How many sexual partners have you had in the past 3 months?

Persons who indicate that they have not had any sexual partners in the past three months are coded as having zero sexual partners.

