MARSSI will be considered to have a positive impact on number of sexual partners in the past three months if the number of sexual partners reported by participants assigned to MARSSI at the three-month post-intervention follow-up is smaller than the number of sexual partners reported by control participants and the difference between groups is statistically significant.

²⁵ We elected to use a three-month recall period for this outcome measure as it measures a behavior that is likely to occur with less frequency than individual acts of sex, and thus represents a quantity that would be easier to recall over a longer period of time.

Table 2. Outcomes used for primary research questions

Outcome name	Source item(s)	Constructed measure	Timing of measure
Frequency of having vaginal sex without condoms in the past 30 days	Participant Questionnaire	
The risk outcome is operationalized as the number of times in the past 30 days a person reports having vaginal sex without using a condom.
 
The measure is calculated from the following item:
 
 • In the past 30 days, how many times have you had vaginal sex without using a condom? 
The resulting variable is continuous with values that range from 0 to k, where 0 indicates that a person has not engaged in vaginal sex without a condom in the past 30 days, and k indicates the number of times the person has engaged in vaginal sex without a condom (risk behavior) in the past 30 days.
 
Note: All respondents who have three-month post-intervention follow-up data and have provided a response to either this question or have indicated they have not had vaginal sex in the past 30 days will be included in the construction of this measure. Persons who indicate that they have not had vaginal sex in the past 30 days are coded as having vaginal sex without a condom zero times.
	Three months post-intervention (four months post-baseline)

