²⁷ This scale construction is based on the work of Higgins, J. A., Popkin, R. A., & Santelli, J. S. (2012). Pregnancy ambivalence and contraceptive use among young adults in the United States. *Perspectives on sexual and reproductive health*, 44(4), 236-243.

Depressive symptoms in the past 2 weeks	Participant Questionnaire	
Participants are asked to indicate for each of the following items how often during the past two weeks they were bothered by:
 
 • Little interest or pleasure in doing things • Feeling down, depressed, or hopeless • Trouble falling or staying asleep, or sleeping too much • Feeling tired or having little energy • Poor appetite or overeating • Feeling bad about yourself, or that you are a failure or have let yourself or your family down • Trouble concentrating on things, such as reading the newspaper or watching television • Moving or speaking so slowly that other people could have noticed. Or the opposite – being so fidgety or restless that you have been moving around a lot more than usual 
Response values are 0=not at all, 1=several days, 2=more than half the days, 3=nearly every day. Scores to all eight items are summed for a summative score.
	Three months post-intervention (four months post-baseline) and six months post-intervention (seven months post-baseline)
Frequency of having vaginal sex in the past 30 days	Participant Questionnaire	
The measure is operationalized as the number of times in the past 30 days a person reports having vaginal sex.
 
The measure is calculated from the following item:
 
 • In the past 30 days, how many times have you had vaginal sex? 
The resulting variable is continuous with values that range from 0 to k, where 0 indicates that a person has not engaged in vaginal sex in the past 30 days, and k indicates the number of times the person has engaged in vaginal sex in the past 30 days.
	Three months post-intervention (four months post-baseline) and six months post-intervention (seven months post-baseline)

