- vii. **Condensed data collection windows.** Our benchmark approach is to include follow-up data from all participants who completed a questionnaire during their open data collection window, regardless of the time point in that window when it was completed. Data collection windows are broad to minimize attrition from the analytic sample. To examine whether or not this influences our results – and, in particular, whether or not study participants who respond later report different outcomes from those who respond earlier – we will conduct an analysis that examines the difference, if any, in response time between treatment and control participants and compares impact estimates for analytic samples without late responders. Late responders will be defined as those participants who complete their long-term questionnaire more than one month after the initiation of the three-month data collection window. We will report any substantive differences in the results section of the final manuscript and analytic findings for both approaches will be presented alongside each other in an appendix.
- viii. **Statistical modeling.** We have proposed using OLS regression as the benchmark statistical method for producing impact estimates. We will conduct analyses to test robustness of this choice and to assess whether there are substantive differences in the point estimates of interest produced by OLS and alternative estimators.⁴⁵ Specifically, for each research question, we will compare OLS estimates with those derived from models that may fit the distribution of the data better. For the two count outcomes (frequency of having vaginal sex without condoms and number of sexual partners), the treatment effect will be estimated with an appropriate count model (using Stata); for the dichotomous outcome, the effect will be estimated using a logit model.⁴⁶ If there is a substantive difference in the impact estimates of interest, we will report the results of each.

h. Bayesian interpretation

In addition to assessing our primary research question findings using a traditional frequentist approach, we will supplement our presentation of impact estimates with a Bayesian interpretation based on posterior probabilities of program effectiveness. To do

⁴⁵ To account for potential violations of model assumptions (e.g., heteroskedasticity, overdispersion), we will use robust standard errors in all analyses.

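### The late-responder rule is keyed to the long-term questionnaire, so excluding late responders does not test lateness on the short-term questionnaire that supplies the primary outcomes

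*SAP*

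**What the plan says.** SAP section 4.g.vii (Condensed data collection windows) explains that the benchmark keeps every response received while the participant's window is open, and that the windows are wide in order to limit attrition. To see whether this affects the results, it plans two things. The first "examines the difference, if any, in response time between treatment and control participants". The second "compares impact estimates for analytic samples without late responders". For the second it defines late responders as "those participants who complete their long-term questionnaire more than one month after the initiation of the three-month data collection window". No other place in the SAP defines late response.

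The follow-up labels are fixed elsewhere:

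- Section 1.a asks all three primary questions at the short-term point: "What is the short-term impact (three months post-intervention) of the offer to participate in MARSSI".
- Section 1.b uses long-term for the later point: "What are the long-term (six months post-intervention period) impacts of the offer to participate in MARSSI". Section 4.b (Outcome measures) does the same.
- Table 2 times each primary outcome at three months post-intervention, which it equates with month 4 after baseline. Table 3 places the six-month point at month 7.

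**The concern.** The rule pairs the long-term questionnaire with a window described as three-month, and three months is the SAP's label for the short-term follow-up. The questionnaire and the window therefore appear to belong to different follow-ups. Whatever the window phrase means, the questionnaire named is not the one that supplies the primary outcomes.

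This is the only one of the eight sensitivity analyses listed in section 4.g that deals with response timing. Its results are to be shown next to the benchmark in an appendix. A reader would take agreement between the two as evidence that late response does not matter for the primary outcomes, and the rule as written cannot supply that evidence.

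**Working it through.** The SAP gives no figure to reproduce here. The check compares definitions and does simple arithmetic on the stated time points.

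**Inputs.** Short-term questionnaire: month 4 after baseline (Table 2). Long-term questionnaire: month 7 after baseline (Table 3). Lateness threshold: more than 1 month after the window opens (section 4.g.vii). Window opening dates are not given, so they are treated as an assumption. Let *s* and *l* be the shifts, in months, of the short-term and long-term openings from months 4 and 7.

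**Reading 1: three-month names the short-term follow-up.**

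- Cut-off = 4 + *s* + 1 = 5 + *s*.
- Earliest long-term completion = 7 + *l*.
- Margin = (7 + *l*) − (5 + *s*) = 2 + *l* − *s*.
- Every long-term completer is late whenever *s* − *l* < 2.

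| Assumed openings | *s* | *l* | Margin (months) |
|---|---|---|---|
| Both on target, or shifted equally | 0 (or *s* = *l*) | 0 | 2.0 |
| Half a month toward each other | +0.5 | −0.5 | 1.0 |
| One month toward each other | +1 | −1 | 0 |

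While the margin is positive, membership of the reduced primary sample depends only on whether the long-term form was returned:

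| Short-term form | Long-term form returned | Long-term form not returned |
|---|---|---|
| On time | excluded | kept |
| Late | excluded | kept |

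The two rows are identical, so lateness on the primary questionnaire plays no part. The sample without late responders consists of people who dropped out before the six-month form.

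**Reading 2: three-month is the length of the window.** The rule is then coherent for the six-month form, with a cut-off of 7 + *l* + 1 = 8 + *l*. Applied to the primary outcomes, it may still remove some participants, but because of when they returned a later form. The overlap between people late on the six-month form and people late on the short-term form is unknown, so no percentage can be given.

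**Common to both readings.** A participant must return the long-term form to be classed as late. Someone who was late on the short-term form and never returned the long-term one cannot be excluded, although that is one of the people the check is meant to find.

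**The case against.** The strongest counter-argument is that the window phrase may describe a duration. The SAP uses a number and unit in that way elsewhere, for example for the two-week booster window in Table 1 and the 30-day and three-month recall periods in section 4.b, and section 4.g.vii itself calls the windows broad. On that reading the sentence is not self-contradictory, and it could serve the six-month versions of the three primary outcomes, which are secondary outcomes under section 1.b. The SAP also uses three-month to name the short-term follow-up in section 4.b, so the text does not settle the matter. The duration reading removes the mismatch between questionnaire and window. It does not supply a lateness rule for the primary questionnaire.

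A second argument is that this is probably a one-word slip, and that an analyst would notice if nearly everyone with long-term data were classed as late. That is plausible. However, there are two natural corrections, changing the questionnaire to short-term or changing the window to six-month. They give different exclusion sets, and only the first serves the primary outcomes. The choice should not be left to whoever runs the analysis.

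It is also fair to say that this is a drafting inconsistency more than a poor choice of method. Dropping late responders and comparing estimates is reasonable, and the one-month threshold is not in dispute.

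**Conclusion.** The concern holds. For the primary outcomes, the exclusion as written does not reflect lateness on the questionnaire that supplies them, under either reading of the window phrase. The stronger result, that every long-term completer is late, belongs to the first reading only. It also assumes that the two window openings converge by less than two months in total, against a nominal margin of 2 months.

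The reach is modest. It affects the exclusion half of one of eight sensitivity analyses. The comparison of response time between arms needs no cut-off and stands. The benchmark does not use the rule. It should be corrected, but it does not threaten the primary analysis.

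**What to change.** Make the questionnaire and the window refer to the same follow-up. Suggested wording for section 4.g.vii: *For the primary outcomes, late responders are participants who complete the short-term (three months post-intervention) questionnaire more than one month after the short-term data collection window opens. Where the check is also run for long-term outcomes, the same rule applies to the long-term questionnaire and the long-term window.*

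The cost is a sentence or two of SAP text. No new data should be needed: the planned comparison of response times implies that completion dates are held, although the SAP does not say so directly. Record the change with its date. Enrollment was to end in April 2023 and the title page is dated October 2023, so nominal month-4 follow-up (April + 4 months = August 2023) had passed by then.

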We have asked an array of secondary and exploratory questions that aim to investigate hypothetical relationships that undergird MARSSI's theory of change. These questions have been designated as subordinate because they are not reviewable by the TPP Evidence Review, because they are ancillary in the theory of change, or because they are not yet understood as confirmatory in the eyes of the program's developers. We investigate these questions to test hypothesized relationships and develop our theoretical understanding of how MARSSI works. Findings to these questions are necessarily of interest to the developers of MARSSI, but may also be generally informative to the field in terms of how a complex intervention like MARSSI influences behavior change. We will report results with interpretation to the program developers for future development and theory refinement. We may also choose to disseminate exploratory results more broadly in the form of peer-reviewed articles, conference papers, or possibly shorter briefs.

Modification to benchmark analytic approach. After receiving written feedback from and discussing options for a benchmark analytic approach with peer reviewers, we have decided to estimate impacts using ordinary least squares (OLS) regression for each of our three primary outcomes. We will use count models as sensitivity tests to test the robustness of those estimates. Any substantive differences between benchmark and sensitivity estimates will be reported in the results section of our impact manuscript.

Correction in the description of blocking variables. In reviewing our analysis plan, we noticed that we had mischaracterized how we intended to construct variables to account for the stratification of random assignment procedures in our analytic models. Prior to random allocation, participants were stratified sequentially into separate pools by: the state in which they indicated they would seek reproductive health care (51 possible options with the inclusion of Washington, DC) and the study coordinator who enrolled them into the study (5 options). Operationally, this has created separate randomization lists for each state-coordinator combination, for a maximum

potential set of 255 separate randomization blocks (51 states * 5 coordinators). In revising this plan, we have clarified that the dummy blocking variables we intend to include in our analytic models reflect this randomization structure.

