We propose to estimate these impacts using a regression-based approach that will model intervention effects as a function of assignment to MARSSI (i.e., treatment), relevant baseline covariates, a baseline measure of the outcome variable, and the combined state and coordinator-level (dummy blocking) indicators (see Table 4 for variable constructions).³⁵ In addition, missing baseline data indicators will be included in the model for each baseline variable in which missing values are imputed through dummy variable adjustment. Although a straight difference-of-means approach should provide unbiased estimates of the effect of the treatment, we propose a model-based approach because it will increase the precision of those estimates and purge any small differences associated with baseline imbalance. The empirical model will be estimated with an OLS regression (using Stata). We present the empirical model here:

$$Y_{Post} = \beta_0 + \beta_1 T + \beta_2 Y_{Pre} + \sum (\beta_p X_p) + \sum (\beta_n D_n) + \sum (\beta_p M_p) + \varepsilon$$

where:

Y_{Post} - The outcome of interest, either: 1) times having vaginal sex without condoms in the past 30 days (continuous; values range 0 to k , where 0= has had sex without condoms 0 times in past 30 days, and k = number of times having vaginal sex without condoms in past 30 days); 2) number of sexual partners in the past 3 months (continuous; values range 0 to k , where 0= has 0 sexual partners in past 3 months, and k = number of sexual partners in past 3 months); or 3) current use of effective non-barrier contraception (dichotomous; where 1= currently using effective non-barrier contraception and 0= not currently using effective non-barrier contraception) reported by participant i three months post-intervention (see Table 2 for full details on the variable construction).

β_0 - The intercept term, which represents, depending on the outcome measure of interest in the analysis, the outcome for the average control participant with all other variables in the model held constant at zero.

β_1 - This is the parameter estimate of substantive interest. β_1 represents, depending on the outcome measure of interest in the analysis, either: 1) the

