X – A p vector of baseline (i.e., measured prior to receiving intervention or exogenous to treatment) participant-level covariates to account for the variation in outcomes associated with these groups. These covariates, listed in detail in Table 4, will include:

- a) Age – self-reported age (based on date of birth) at screening (continuous; range 16-21); variable will be re-centered at the grand mean for analysis.
- b) Gender – gender of participants as self-reported at baseline (coded as 1 if female and coded as 0 if otherwise); variable will be re-centered at the grand mean for analysis.
- c) Race – race of participant as self-reported at baseline (coded as 1 if participant self-identified as only White and 0 if otherwise); variable will be re-centered at the grand mean for analysis.
- d) Ethnicity – Hispanic/Latino(a) ethnicity of participant as self-reported at baseline (coded as 1 if identify as Hispanic/Latino(a) and 0 if do not identify as Hispanic/Latino(a)); variable will be re-centered at the grand mean for analysis.

D – An $n-1$ vector of blocking variables (i.e., subgroups within which random assignment occurred), where n represents the full enumeration of all state-by-coordinator blocks from which participants were randomly assigned to condition. For each of these n coordinator-by-state blocks, we include in the analytic model a dummy indicator variable that will identify whether a study participant was randomized within that block (1) or not (0). The variables will be re-centered at the grand mean for analysis.

M – A p vector of missing baseline data indicator variables representing each of the p baseline covariates that had missing observations (coded as 1 if the observation for that variable is missing and 0 if it is non-missing).

Using a vector of dummy variables (LSDV) in a regression to account for a blocked randomization scheme is a conventional choice for a situation where each block has the same probability of assignment.³⁶ This is consistent with our design specification and so we have adopted the dummy variable modeling strategy here. As Angrist (1998) and others have pointed out, however, scenarios exist where the strategy may fail to identify the estimand of interest for a variety of reasons. Of particular interest

³⁶ Gerber, A. S., & Green, D. P. (2012). *Field Experiments: Design, Analysis and Interpretation*. W.W. Norton & Company.

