here is that the dummy-blocking scheme may exclude blocks/cases from the full randomized sample. Regardless of what the nominal randomization probabilities may be, one feature of the blocking model is that it will assign zero weight to any block partition where the actualized probability of treatment equals 0 or 1. That is, study assignment blocks that contain only a single participant (who is then assigned to either treatment or control) are functionally excluded from the treatment effect estimate.

If this is pervasive enough in the analytic sample – where multiple cells exist with just a single participant – impact estimates may fail to identify the treatment effect for the fullest possible ITT sample. In this case we will alter our benchmark approach and substitute the LSDV procedure with an almost-equivalent inverse-probability-of-treatment-weighted (IPTW) regression, which should mitigate the exclusion problem, while still weighting cells accordingly. This estimation approach is almost equivalent to the LSDV blocking procedure except that it is functionally saturated with respect to the treatment and dummy variables (but not covariates), and it can be constructed to broaden the analytic sample to include cells where only a single case was randomized and (calculated) probability of treatment is 0 or 1.³⁷ When we use a normalized IPTW and estimate the propensity score with the linear probability model the single-case blocks are given reduced but not zero weight.

If we use the IPTW regression as the benchmark approach, we will weight each observation by the inverse probability of assignment for their condition in their block. For the treatment group, the weights will be $\frac{1}{e(x)}$; for the control group, weights will be $\frac{1}{1-e(x)}$. Where $e(x)$ is the propensity score estimated by the linear probability model using the following specification:

$$e(x) = \alpha_0 + \sum (\beta_n D_n) + \varepsilon$$

Prior to estimation we will normalize weights such that the sum of all weights will be equal to 1.

We will report model-estimated effects and the results of significance tests in the findings section of the final impact report. Statistical significance will be based on test statistics produced by Stata for the coefficient β_1 using a two-tailed test, with $p < .05$.

ii. Adjustment for baseline differences

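### If the block-dummy model is kept with Stata's default robust variance, participants alone in their block widen the primary standard errors by sqrt(N/(N−s)) without informing the effect

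*SAP*

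**What the plan says.** Section 4.e.i (Estimation approach) fits one OLS model in Stata to each primary outcome. It contains treatment, the baseline outcome, four demographic covariates, missing-data indicators and block dummies. On the dummies it says "For each of these n coordinator-by-state blocks, we include in the analytic model a dummy indicator variable", "where n represents the full enumeration of all state-by-coordinator blocks from which participants were randomly assigned to condition". The Introduction and Table 4 put the maximum at 51 × 5 = 255 blocks. Significance is judged two-sided at 0.05 on Stata's test statistic for the treatment coefficient.

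The variance choice appears only in footnote 45 to section 4.g.viii: "we will use robust standard errors in all analyses". No type of robust variance is named.

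Section 4.e.i also says of the block-dummy model that "it will assign zero weight to any block partition where the actualized probability of treatment equals 0 or 1", and that blocks holding one participant "are functionally excluded from the treatment effect estimate". It treats this as a question of which sample the estimate represents. If such blocks are widespread, the plan is: "In this case we will alter our benchmark approach and substitute the LSDV procedure with an almost-equivalent inverse-probability-of-treatment-weighted (IPTW) regression". No threshold is given.

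**The concern.** The SAP sees that a participant alone in a block cannot inform the treatment coefficient. It does not follow the same participant into the variance, where that person still counts in the sample size used by the finite-sample factor. The reported standard error is then larger than the data behind the estimate warrant.

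The SAP justifies regression adjustment by precision, and this hands some of that precision back. Other parts of the plan use the same result. Section 4.f applies the benchmark approach to the full-sample secondary outcomes. Section 4.h weights the estimate by its precision, so a larger standard error pulls it further toward the prior. Section 5 opens the mediation analyses only if p < .05.

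**Working it through.** **Inputs.** From the SAP: OLS in Stata, one dummy per occupied block, at most 255 blocks, robust standard errors, two-sided 0.05, 1:1 allocation. Assumed, because the SAP is silent: Stata's default robust form (HC1), the number analysed N, and the share s/N of analysed participants who are alone in their block. The SAP gives no sample size or power figure to reproduce.

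**Step 1. The variance.** With K fitted parameters,

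V(HC1) = [N/(N−K)] × sandwich.

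**Step 2. What one single-participant block does.** Its own dummy fits that participant exactly. The residual is 0, and treatment after removing blocks and covariates is also 0. So:

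- the treatment coefficient and covariate slopes do not change;
- the sandwich term for treatment does not change;
- N rises by 1 and K rises by 1, so N−K, and hence the t reference distribution, does not change;
- only the numerator N of the factor rises.

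With s such participants,

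SE(all rows) / SE(without them) = sqrt{[N/(N−K)] / [(N−s)/(N−K)]} = sqrt(N/(N−s)).

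This is algebra and holds for the count outcomes and the binary outcome alike. Numerical fits agreed: coefficients matched to rounding error, and one fit gave an SE ratio of 1.0660138 against the same value from the formula.

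**Step 3. Size.** Let r = sqrt(1/(1−s/N)). If the SE without singletons is correct, power is Φ(2.80/r − 1.96) and type I error is 2[1−Φ(1.96r)].

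| s/N (assumed) | r | Power if nominally 80% | Type I error |
|---|---|---|---|
| 2% | 1.010 | 79.2% | 4.8% |
| 5% | 1.026 | 78.0% | 4.4% |
| 10% | 1.054 | 75.7% | 3.9% |
| 15% | 1.085 | 73.3% | 3.4% |
| 20% | 1.118 | 70.7% | 2.8% |

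**Step 4. Which of the two standard errors is closer to the truth?** Simulation under no effect, using the SAP's model, 255 potential blocks, assumed permuted blocks of 2/4/6 and 1,500 replicates. Each cell gives root-mean-square SE over true SD, then the null rejection rate.

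| Outcome, N, singletons | All rows | Singletons removed |
|---|---|---|
| Normal, 250, 12% | 1.089, 3.4% | 1.021, 4.4% |
| Normal, 250, 26% | 1.152, 2.3% | 0.992, 4.9% |
| Count, 500, 11% | 1.050, 3.2% | 0.988, 5.0% |
| Binary, 500, 11% | 1.053, 3.9% | 0.991, 5.1% |
| Normal, 1000, 3% | 1.016, 4.1% | 0.999, 4.6% |

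The simulated SD has a relative Monte Carlo error of about 1/sqrt(3000) = 1.8%, so the last row's 1.016 cannot be told from 1 by simulation alone. The ratio between the columns follows from Step 2 and does not depend on simulation.

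A further 700-replicate run let the residual SD in small blocks be 0.5 to 2.5 times that in large blocks. SE over true SD was 1.005 to 1.119 with all rows and 0.962 to 1.053 with singletons removed. Null rejection was 2.9% to 4.4% and 3.4% to 5.9% respectively.

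**Step 5. Larger one-arm blocks.** Covariates are in the model, so a one-arm block of two or more helps estimate their slopes and is not exactly zero-weight. Adding a one-arm block of m people raises the factor only if (N+m)/(N−K+m−1) > N/(N−K), that is, if m < N/K. Removing these blocks as well moved the SE ratio by only about 0.002 to 0.012.

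**The case against.** The strongest reply is that the plan already provides for this. Section 4.e.i identifies single-participant blocks and moves to a weighted regression if they are widespread, and that move removes the mechanism. If the block-dummy model survives only when such blocks are few, the loss is 1% to 3% of the standard error. That stands in part. With no threshold, however, the block-dummy model could be kept with a material share of singletons.

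Enrolment may also be more concentrated than feared. It began with Planned Parenthood patients in seven states (footnote 7), and active recruitment ran through partner affiliates. Assuming 90% of participants come from seven states, with 85% retention and unequal coordinators, the inflation is 4.5% at 300 randomised, 3.6% at 500, 3.0% at 800 and 2.3% at 1,200. These figures rest on assumptions as well, but they show that a small effect is plausible.

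The SAP also names no robust variance type. An HC2 form does not use this factor and was close to calibrated in the 700-replicate run (0.980 to 1.053). This stands: the point is conditional on HC1.

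A reader might go further and remove every one-arm block. The SAP's description of zero weight could suggest it, but Step 5 shows that it holds exactly only for singletons once covariates are included. Wider removal would drop randomised responders for almost no gain.

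**Conclusion.** The point holds on three conditions: the block-dummy model stays the benchmark, Stata's default robust variance is used, and some analysed participants are alone in their block. The standard error for each primary outcome is then sqrt(N/(N−s)) times what the informative rows give. That is 1% to 3% for singleton shares of 2% to 5%, 5.4% at 10% and 11.8% at 20%. At 20%, the loss from a nominal 80% power is about nine percentage points.

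A reader might infer that the primary intervals are certainly too wide, or that power falls into the mid-60s. The documents do not support either. They give no N, no count of occupied blocks and no variance type, and very high singleton shares are where the weighted regression would probably replace this model. Nor is there a risk of false positives from this source: the error is conservative and leaves the estimate unchanged. It is a modest, avoidable loss of power.

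**What to change.** Add to section 4.e.i and footnote 45: whenever the block-dummy model is used, robust standard errors are computed after removing blocks that contain a single participant in that outcome's analytic sample; the number removed is reported for each outcome. Name the robust variance type in the same sentence. The count must be taken after cases with missing outcomes are deleted, because deletion can leave a participant alone in a block.

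The cost is that sentence and one line of code. The treatment estimate and residual degrees of freedom are identical. The model N is slightly smaller, so report the full ITT analytic N beside it. Larger one-arm blocks can stay in the fit. Fixing this before analysis also avoids choosing between two standard errors for one estimate once results are known.
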